8.1 EFFICACY ASSESSMENTS

Planned time points for all efficacy assessments are provided in the SoA.

The assessment of antitumor activity of tusamitamab ravtansine combined with ramucirumab with regard to ORR per RECIST 1.1 is the primary efficacy objective.

All participants treated must have at least one measurable lesion as per RECIST 1.1 for inclusion based on tumor assessment defined in the SOA, [Section 1.3](#).

Tumor assessment will be made every 6 weeks (± 7 day window), and a scheduled assessment time point will not be modified in case of a cycle delay. Thoracic-abdominal-pelvic CT-scan or MRI and any other examinations as clinically indicated will be performed to assess disease status at baseline; then every 6 weeks during the study treatment period until radiological disease progression, initiation of further anticancer therapy, death, or study cut-off for secondary endpoints, whichever comes first; and at the end of study treatment, except if already done at last cycle. Confirmatory radiological evaluation will be performed at least 4 weeks after initial documentation of response. After IMP discontinuation, tumor assessment should be performed at EOT for patients without imaging performed within past 4 weeks, and every 8 weeks (± 7 days) after the last tumor assessment until disease progression or initiation of a new anticancer treatment, death, or the study cut-off for secondary endpoints, whichever comes first. Brain

CT-scan or MRI should be performed at baseline and followed only for patients with brain lesions at baseline. Imaging assessments during the on-treatment period are to be scheduled using the Cycle 1, Day 1 date as the reference date for all time points, and are not to be scheduled based on the date of the previous imaging time point. Delay of an imaging assessment to conform to treatment delay is not permitted. The same tumor assessment technique must be used throughout the study for a given lesion/participant.

Secondary efficacy endpoints will include DOR, PFS, and DCR.

The RECIST 1.1 criteria will be followed for assessment of tumor response; see Appendix 13 ([Section 10.13](#)) for details.

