9.2 POPULATIONS FOR ANALYSES

The following populations for analyses are defined in [Table 9](#):

Table 9 - Populations for analyses

Population	Description
Prescreened	All participants who signed the prescreening informed consent for CEACAM5 assessment of their biopsy.
Screened	All participants who signed screening informed consent for study participation.
Enrolled	Participants from screened population who have been allocated to intervention regardless of whether the intervention was received or not.
All-treated	All enrolled participants exposed to the study treatment, regardless of the amount of treatment administered. This population is the primary population for all efficacy parameters.
DLT-Evaluable (Part1)	All enrolled participants who received 2 cycles with at least 80% of the intended dose for both tusamitamab ravtansine and ramucirumab at each of the first 2 infusions unless they discontinued the study intervention before the end of Cycle 2 due to a DLT.
Activity	All treated participants who have measurable disease at study entry and at least 1 postbaseline evaluable tumor assessment. Participants with no postbaseline evaluable tumor assessment but with an early clinical progression or who died from disease progression will also be included in this set. This population is the secondary population for all efficacy parameters.
PK	All participants from the all-treated population with at least 1 postbaseline PK concentration (whatever the cycle and even if dosing is incomplete) with adequate documentation of dosing and sampling dates and times.
ATA	All participants from the all-treated population with at least 1 postbaseline ATA result (negative, positive or inconclusive).

Abbreviations: ATA = antitherapeutic antibody; CEACAM5 = carcinoembryonic antigen-related cell adhesion molecule 5; DLT = dose-limiting toxicity; PK = pharmacokinetic.

Participants exposed to study intervention before or without being enrolled will not be considered enrolled and will not be included in any analysis population. The safety experience of these participants will be reported separately.

Enrolled participants for whom it is unclear whether they took the study intervention will be considered as exposed and will be included in the safety population.

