# 2 ANALYSIS POPULATIONS

The following populations for analyses are defined:

Population	Description		
Prescreened	All participants who signed the prescreening informed consent for CEACAM5 assessment of their biopsy.		
Screened	All participants who signed the screening informed consent for study participation.		
Enrolled	Participants from screened population who have been allocated to intervention regardless of whether the intervention was received or not.		
All-treated	All enrolled participants exposed to the study treatment, regardless of the amount of treatment administered. All safety analyses will be performed on this population, which is also the primary population for analysis of all efficacy parameters.		
DLT-evaluable (Part 1)	All enrolled participants who received 2 cycles with at least 80% of the intended dose for both tusamitamab ravtansine and ramucirumab at each of the first 2 infusions. Any participant who experienced a DLT during that period will also be DLT-evaluable.		
Activity	All-treated participants who have measurable disease at study entry and at least 1 postbaseline evaluable tumor assessment. Participants with no postbaseline evaluable tumor assessment but with an early clinical progression or who died from disease progression will also be included in this set. This population is the secondary population for analysis of efficacy parameters.		
Pharmacokinetic (PK)	All participants from the all-treated population with at least 1 postbaseline PK concentration (whatever the cycle and even if dosing is incomplete) with adequate documentation of dosing and sampling dates and times.		
ATA	All participants from the all-treated population with at least 1 postbaseline ATA result (negative, positive, or inconclusive).		
Population without trial impact	All treated participants:		
(disruption) due to COVID-19	
 
without any critical or major deviation related to COVID-19
 
		
	
 
and who did not permanently discontinue treatment due to COVID-19
 
		
	
 
and who did not permanently discontinue study due to COVID-19.
 
		

Table 4 - Populations	for analyses
-----------------------	--------------

In practice, a participant will be included in the enrolled population if the question "Will the subject continue in the treatment phase?" has been answered "Yes" in the "Completion of screening phase" e-CRF page.

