In practice, a participant will be included in the DLT-evaluable population (applicable to Part 1 only) if a "Dose Limiting Toxicities" e-CRF page has been filled in at the end of Cycle 1 and at the end of Cycle 2 (or Cycle 1 only if participant did not receive Cycle 2 because of a DLT). This includes any participant followed up to the end of the DLT observation period, or having experienced a DLT before the end of the DLT observation period and validated by the Study Committee. A participant with an overdose (defined as a dose received at least 30% above the intended dose) of tusamitamab ravtansine or ramucirumab at any of the 2 first infusions will be excluded from the DLT-evaluable population.

Statistical Analysis Plan SAR408701-ACT16444 - tusamitamab ravtansine 17-Jul-2023 Version number: 1

Participants exposed to study intervention before or without being enrolled will not be considered enrolled and will not be included in any analysis population. The safety experience of these participants will be reported separately. Enrolled participants for whom it is unclear whether they took the study intervention will be considered as exposed and will be included in the all-treated population.

For any participant enrolled more than once, only the data associated with the first enrollment will be used in any analysis population. The safety experience associated with any later enrollment will be reported separately.

In practice, participants whose BOR is nonevaluable due to minimum criteria for SD duration not met (ie, overall response of SD and the minimum duration, defined as 0.75 x duration between the first IMP intake and the first planned tumor assessment is not met) and there is no subsequent evaluable tumor assessment, or documented PD after two or more non-evaluable tumor assessments (ie, overall response of PD and the time between the date of first IMP intake and the documentation of PD is greater than the theoretical planned date of the second tumor assessment) will be considered as not evaluable for the activity population.

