### 3.2.2 Main analytical approach

#### 3.2.2.1 Confirmed objective response

The primary efficacy analysis is based on the primary estimand for part 2 introduced in Section 1.2.1. This primary estimand is defined according to the following attributes:

- The primary efficacy endpoint is confirmed objective response (confirmed CR or PR as BOR) as per RECIST 1.1. based on the investigator's assessment as defined in Section 3.2.1.2.
- The treatment condition of interest is tusamitamab ravtansine loading dose Q2W in combination with ramucirumab.
- The analysis population is the participants from all-treated population (defined in Section 2) treated at the RD of tusamitamab ravtansine loading dose Q2W regimen (ie, excluding participants treated at the starting dose, if this differs from the RD).
- Intercurrent events:
  - The study intervention discontinuation intercurrent event will be handled with the treatment policy strategy. Confirmed objective response will be assessed based on tumor assessments regardless of study intervention discontinuation.
  - The further anticancer therapy (including further systemic anticancer therapies) intercurrent event will be handled with the "while not initiating further anticancer therapy" strategy. Confirmed objective response will be assessed based on tumor assessments done up to the time of initiation of further anticancer therapy.

• The population-level summary will be the ORR, defined as the rate of participants with confirmed objective response and 2-sided 95% CIs using the Clopper-Pearson method.

In the absence of confirmed objective response before the analysis cut-off date (taking into account the intercurrent event handling strategies), participants will be considered as non-responders, whatever the reason (including participants with missing or non-evaluable BOR).

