# 3.2.4 Supplementary analyses

Number (%) of participants within each BOR category, including not evaluable as per RECIST 1.1 and reason for being not evaluable will be provided on the subgroup of participants from the all-treated population treated at the RD (ie, excluding participants treated at the starting dose if this differs from the RD).

As a supplementary analysis, confirmed objective response as per RECIST 1.1 will also be summarized on the subgroup of participants from activity population (defined in Section 2) treated at the RD for tusamitamab ravtansine in a loading-dose Q2W regimen (ie, excluding participants treated at the starting dose if this differs from the RD). The same analytical approach as described above will be used.

In addition, the best relative tumor change from baseline, defined as the smallest relative tumor change from baseline (where tumor change at time t is the difference between sum of the longest diameters of the target lesions at time t and baseline, resulting in a negative value in case of decrease), will be summarized using a waterfall plot on the participants on the all-treated population treated at the RD (ie, excluding participants treated at the starting dose if this differs from the RD). A swimmer plot will also be provided reporting the duration of treatment for all participants with their overall response and some baseline characteristics. This plot will differentiate responders from non-responders. In addition, a spider plot will also be provided reporting the tumor change from baseline over the time.

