# 3.3.2.2.2 Progression-free survival

PFS analysis is based on an estimand defined according to the following attributes:

- The endpoint is progression-free survival.
- The treatment condition of interest is tusamitamab ravtansine loading dose Q2W in combination with ramucirumab.
- The analysis population is the participants from the all-treated population (defined in Section 2) treated at the RD of tusamitamab ravtansine in a loading-dose Q2W regimen (ie, excluding participants treated at the starting dose if this differs from the RD).
- Intercurrent events:
  - The study intervention discontinuation will be handled with the treatment policy strategy. PFS will be assessed based on tumor assessments regardless of study intervention discontinuation.
  - The further anticancer therapy (including further systemic anticancer therapies) intercurrent event will be handled with the hypothetical strategy. PFS will be assessed based on tumor assessments had a further anticancer therapy not been taken. PFS will be assessed based on tumor assessments up to the time of initiation of further anticancer therapy.
  - Two or more consecutive missing/unevaluable tumor assessments immediately before documented PD or death will be handled with the hypothetical strategy. PFS will be assessed based on tumor assessments had 2 consecutive tumor assessments not been missed immediately before documented PD or death. PFS will be assessed based on tumor assessments up to the last evaluable tumor assessment documenting no progression.
- The population-level summary will include:
  - Kaplan-Meier estimates of the 25th, 50th, and 75th percentiles and their associated 95% CIs using a log-log transformation of the survival function and the method of Brookmeyer and Crowley.

- Number (%) of participants at risk as well as the probabilities of being event-free at least at 3, 6, 9, and 12 months with 95% CIs using the Kaplan-Meier method and a log-log approach based on a normal approximation following the Greenwood's formula.
- Kaplan-Meier curve including the number of participants at risk at key time points.

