# 3.3.2.2.3 Disease control rate

DCR analysis is based on an estimand defined according to the following attributes:

- The endpoint is disease control response (confirmed CR or PR or SD as BOR) as per RECIST 1.1.
- The treatment condition of interest is tusamitamab ravtansine loading dose Q2W in combination with ramucirumab.
- The analysis population is the participants from all-treated population (defined in Section 2) treated at the RD of tusamitamab ravtansine loading-dose Q2W regimen (ie, excluding participants treated at the starting dose if this differs from the RD).
- Intercurrent events:
  - The study intervention discontinuation will be handled with the treatment policy strategy. Disease control response will be assessed based on tumor assessments regardless of study intervention discontinuation.
  - The further anticancer therapy (defined as all further systemic anti-cancer therapies) intercurrent event will be handled with the "while not initiating further anticancer therapy" strategy. Disease control response will be assessed based on tumor assessments done up to the initiation of further anticancer therapy.
- The population-level summary will include the disease control rate, defined as the rate of participants with disease control response and 2-sided 95% CIs using the Clopper-Pearson method.

In the absence of confirmed objective response and SD before the analysis cut-off date (taking into account the intercurrent event handling strategies), participants will be considered as non-DCR, whatever the reason (including participants with non-evaluable BOR).

Disease control rate will also be summarized on the activity population as a supplementary analysis.

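### The SAP's practical rule removes participants with late documented progression from the activity population, against its own Table 4, and its date test also catches on-schedule second scans

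*SAP*

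**What the plan says.** Protocol Section 9.2 (Table 9) defines the activity population as "All treated participants who have measurable disease at study entry and at least 1 postbaseline evaluable tumor assessment". SAP Section 2 (Table 4) repeats this and widens it: "Participants with no postbaseline evaluable tumor assessment but with an early clinical progression or who died from disease progression will also be included". The sample-size text (Protocol 9.1, SAP 4) describes participants evaluable for activity in the same terms.

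Below Table 4, the last paragraph of SAP Section 2 lists participants with nonevaluable BOR who are to be left out. There are two branches:

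- **Short stable disease.** Stable disease recorded before 0.75 times the interval to the first planned scan, with no later evaluable scan.
- **Late progression.** Progression documented after at least two non-evaluable scans. The parenthesis that defines this asks only whether the time from first dose to progression "is greater than the theoretical planned date of the second tumor assessment) will be considered as not evaluable for the activity population".

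On-treatment scans are due every 6 weeks, plus or minus 7 days, and "are to be scheduled using the Cycle 1, Day 1 date as the reference date for all time points" (Protocol 8.1).

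The activity population carries two supplementary analyses. For response, "confirmed objective response as per RECIST 1.1 will also be summarized on the subgroup of participants from activity population" (SAP 3.2.4). DCR is repeated on it as well (SAP 3.3.2.2.3).

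**The concern.** The practical rule excludes people whom both population tables include. Someone who dies of disease progression without any evaluable scan stays in, while someone whose progression is documented on a scan goes out. The SAP version history records changes to the estimands and to the DLT-evaluable population, but not this narrowing of the protocol's definition.

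The date test does not count scans and makes no allowance for the scan window, so it can label a participant as having lost two scans when only one was lost.

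The effect runs in one direction. A participant without an evaluable BOR is a failure for both endpoints: for ORR, "participants will be considered as non-responders, whatever the reason (including participants with missing or non-evaluable BOR" (SAP 3.2.2.1); for DCR, "participants will be considered as non-DCR, whatever the reason (including participants with non-evaluable BOR" (SAP 3.3.2.2.3). Taking such participants out lowers the denominator and leaves the numerator alone. A programmer working from Table 4 and one working from the practical rule would also report different denominators.

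**Working it through.** **1. Is a progression scan evaluable?** Table 14 in Protocol Appendix 13 lists progressive disease as an overall response, separate from the inevaluable category. The SAP rule itself describes these cases as having an overall response of progression. They therefore have at least one evaluable postbaseline scan and, with measurable disease, belong in the Table 4 population.

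**2. Scan calendar.** Inputs from Protocol 8.1: interval 42 days, window ±7 days, counted from first dose. Scan k is planned at day 42k.

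| Scan | Planned day | Window (days) |
|---|---|---|
| 1 | 42 | 35–49 |
| 2 | 84 | 77–91 |
| 3 | 126 | 119–133 |

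This reproduces the plan's own timing: 84/7 = 12 weeks for two assessments, and 12 + 4 = 16 weeks with confirmation (SAP 3.1).

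**3. Date test on an on-schedule scan 2.** The test is days to progression > 84. Within days 77–91 it is met on days 85, 86, 87, 88, 89, 90 and 91, which is 7 of the 15 permitted days. (If Cycle 1 Day 1 is numbered Day 1, these are study days 86–92.) On those days only scan 1 can have been lost among scheduled scans, so the stated condition of at least two is not met.

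**4. Same participant under the PFS rule.** Suppose scan 1 is missed and progression is seen on day 88. SAP 3.3.2.2.2 says: "Two or more consecutive missing/unevaluable tumor assessments immediately before documented PD or death will be handled with the hypothetical strategy". Only one scan is missing, so that rule does not apply and the progression counts as a PFS event. Under the date test the same progression makes the participant not evaluable for activity.

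**5. Short stable-disease branch.** The threshold is 0.75 × 42 = 31.5 days, which is before the scan 1 window opens on day 35. The branch can still be reached on schedule. The end-of-treatment visit is 30 ± 5 days after the last infusion, and Protocol 8.1 requires a scan there if none was done in the previous 4 weeks. After a single infusion that visit falls on about days 25–35, partly before 31.5.

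**6. Size.** With x successes among n participants and k exclusions, all of them failures, the rate moves from x/n to x/(n − k), which is never lower. The documents give no counts. The table assumes n = 32 and k = 1 to 4; intervals are Clopper-Pearson 95%.

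| Endpoint | x | x/32 | x/31 | x/28 |
|---|---|---|---|---|
| ORR | 0 | 0% (0–10.9) | 0% | 0% (0–12.3) |
| ORR | 3 | 9.4% (2.0–25.0) | 9.7% | 10.7% (2.3–28.2) |
| ORR | 6 | 18.8% (7.2–36.4) | 19.4% | 21.4% (8.3–41.0) |
| ORR | 9 | 28.1% (13.7–46.7) | 29.0% | 32.1% (15.9–52.4) |
| DCR | 16 | 50.0% | 51.6% | 57.1% |
| DCR | 20 | 62.5% (43.7–78.9) | 64.5% | 71.4% (51.3–86.8) |
| DCR | 24 | 75.0% | 77.4% | 85.7% |

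**The case against.** The best defence is that Table 4 leaves the term evaluable undefined and the practical paragraph supplies the definition, as the SAP does for the enrolled and DLT-evaluable sets. The protocol leaves technical detail to the SAP, and Appendix 13 asks the analysis plan to say how missing assessments are handled. On this reading the specific sentence governs. That does not remove the conflict. A SAP sentence that drops participants with a documented response category narrows the protocol's population, and neither the Table 4 row nor the version history says so.

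A second defence is that one missed scan followed by progression on day 88 does not meet the rule's words, so only the parenthesis catches it. That is correct, but the parenthesis is the only operational definition given, and SAP 3.2.1.2 refers only to RECIST 1.1 for deriving BOR. If the words prevail, the parenthesis is wrong; if the parenthesis prevails, on-schedule scans are caught.

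A third point is about the starting denominator. If the planned 32 are counted after exclusions, the comparison is 6/32 = 18.8% against 6/33 = 18.2% to 6/36 = 16.7%. The direction is the same and the gap is similar.

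Several limits stand. A participant with valid stable disease at scan 1 keeps that as BOR and is not touched. The figure of 7 days in 15 is not a probability. The PFS and DOR rule names consecutive lost scans but gives no counting algorithm. SAP 3.2.4 tabulates nonevaluable BOR with reasons in the all-treated set at the recommended dose, so the number of such cases will be visible.

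**Conclusion.** The concern holds on both counts. The practical rule contradicts SAP Table 4 and Protocol Table 9, and its date test contradicts its own stated condition for progression on days 85–91.

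The reach is limited to the supplementary ORR and DCR. The primary ORR and the main DCR use all treated participants at the recommended dose and do not change. The bias is upward or nil. On assumed counts of one to four exclusions from 32, ORR rises by 0 to about 4 percentage points (nil with no responders; 28.1% to 32.1% with 9) and DCR by about 1.6 to 10.7 points (50.0% to 51.6%; 75.0% to 85.7%). The responder, control and exclusion counts are all assumptions, and the documents do not allow the frequency of exclusions to be estimated. This should be corrected before the analysis, but it does not threaten the primary result.

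**What to change.** - Delete the late-progression exclusion from the last paragraph of SAP Section 2. Participants with documented progression then stay in the activity population as non-responders without disease control, as Table 4 and Protocol Table 9 provide.
- Reconcile the short stable-disease branch with Table 4: either delete it or write it into the Table 4 definition.
- If a late-progression flag is still wanted for deriving BOR, define it by the actual number of consecutive missing or non-evaluable scans before progression, in line with the PFS and DOR rule, and not by the planned date of scan 2.

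The cost is one edited SAP sentence and no new data. The supplementary ORR and DCR may come out slightly less favourable.
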